4.4 Sample size calculation

The primary objective of the trial is to validate the prediction that a higher response (lower mean P-SCCAI score) is induced at T= 8 weeks by the prebiotics intervention in mild UC patients with low Bacteroidetes levels (predicted responders), but not in those with high Bacteroidetes levels (predicted non-responders) in their gut. Mild UC is defined as a P-SCCAI score of 3 to 5. According to an extensive study regarding UC disease activity conducted in the Netherlands, mild UC patients have a P-SCCAI score of 3.5 ± 0.5 (Mean \pm standard deviation (SD)), and patients in remission score at 1.0 ± 0.33 (Mean \pm SD)[34, 35].

In a series of germinated barley foodstuff (GBF) intervention studies, 10 mild to moderately active UC patients received 30 grams of GBF (equals to 10 grams fiber) daily for 4 weeks [4], and researchers found a significant decrease in clinical activity index scores. In a later study, another group of 11 mildly to moderately active UC patients consuming 20-30 grams of GBF (equals to 6.66-10 g fiber) daily for 4 weeks showed similar results, with decreases in clinical activity index scores [28].

Based on two-sided statistical testing for unpaired continuous data, an $\alpha=0.05$ (chance on type-I error) and $\beta=0.10$ (chance on type-II error), and assuming a 20% difference of mean P-SCCAI score between predicted responders with prebiotics and predicted non-responders with prebiotics, it was calculated that at least 11 subjects per group are needed for the primary outcome P-SCCAI ($\mu_1=3.5$; $SD_1=0.5$; $\mu_2=2.8$). According to previous trials on prebiotics on IBD patients, a 20% of drop-out rate is commonly seen. Given that the intervention duration is 8 weeks long, followed by a 1 year follow-up, higher dropout rate (30%) is expected. To compensate for a 30% drop-out rate, 15 subjects per group are needed.

To reach inclusion of 30 predicted responders and 30 predicted non-responders, we made an estimate how many subjects we need to screen based on the earlier obtained microbial composition of stool samples from UC patients in the Ede area. Around 50% of these subjects were categorized as low Bacteroidetes subjects (predicted responders) and while 17% of them as high Bacteroidetes subjects (predicted non-responders). To include these responders we will need to screen 177 mild UC patients.

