10. STATISTICAL ANALYSIS

Statistical analyses will be done using the statistical program embedded within R. The threshold for significance will be set at $p<0.05$, with a FDR correction for 16S rRNA gene sequence data. In general, the continuous data will be presented as mean \pm standard deviation or mean and interquartile range when skewed, and categorical data as counts and percentages. Normality will be checked by visual inspection and QQ plots, followed by the Shapiro Wilk test for testing if data show a normal distribution.

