10.2 Secondary study parameter(s)

Response over time

To assess the response over time, data of mean P-SCCAI score within each arm at T = 0, 4, 8, 12 and 60 weeks will be obtained. Comparisons will be made between groups (as done for T = 8 for the primary study parameter) as well as within subjects over time. With P-SCCAI score ≤ 2 being regarded as clinical remission, and a decrease in the P-SCCAI score by more than two points from baseline being regarded as clinical response, we will determine whether subjects have reached clinical remission and/or showed a clinical response over time.

To assess the response within each subject (clinical remission and/or clinical response) over time, data of sum P-SCCAI score within each subject at T = 0, 4, 8, 12 and 60 weeks will be obtained. For comparative analyses between baseline and intervention, the parametric paired sample T-test or the non-parametrical Kruskal-Wallis or Mann-Whitney

U test will be used, depending on the distribution of the samples. Differences between treatments before and after supplement intake will also be analysed by linear mixed models for repeated measures, using “treatment” [prebiotics/placebo], “responding” [responders/non-responders], “time point” [0, 4, 8, 12 and 60 weeks] and “treatment x responding x time point” as fixed effects and subject as random effect. Clinically relevant variables such as BMI, age, sex, and medication use will be taken into account.

Mucosal inflammation

Fecal calprotectin data will be analysed in the same manner as described above (Response over time).

GI complaints:

Data from GSRS will be computed into scores, and the score of each item will be pooled together as the sum score, and the score of each item within each domain will be pooled as well. All data will be analysed in the same manner as described above (Response over time). Differences over time within and between groups will be tested with mixed model analysis. Variables such as timepoint, group, age, sex will be taken into account.

Stool consistency and frequency

Average bowel movement per day and dynamic change on stool consistency will be calculated and collected. All data will be analysed in the same manner as described above (Response over time)..

Gut microbiota and SCFAs

Fecal SCFAs data will be analysed in the same manner as described above (Response over time)

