16S rRNA gene sequencing provides sequence read counts data. It will be normalized to microbial relative abundance, and microbiota diversity indices (Shannon, Simpson, and inverse Simpson) are calculated at amplicon sequence variant (ASV) level, as implemented in the Picante [66] and Phyloseq [67] packages in R, respectively. Wilcoxon test will be applied to determine whether diversity as well as the relative abundance of specific bacterial taxa, were significantly different between groups since the data was non-parametric. For microbiota analysis, *p*-values will be corrected for multiple comparisons using the Benjamini–Hochberg procedure. To correct for a false discovery rate (FDR), a FDR adjusted *p*-values will be computed, a so-called *q*-value [68]. A corrected *q*-value of less than 0.2 was considered significant. Paired tests will be used to

compare the effects of prebiotics. Pairwise weighted UniFrac [69] and unweighted UniFrac [70] distance-based principle coordinate analysis (PCoA) will be used to visualize microbial community variation at the ASV level. Permutational multivariate analysis of variance (PERMANOVA) will be used to test for significant differences between groups, as implemented in the Vegan package [71].

Health-related quality of life

Data from SIBDQ will be computed into scores, and the score of each item will be pooled together as the sum score, and the score of each item within each domain will be pooled as well. All data will be analysed in the same manner as described above (Response over time).

Medication use

Type, Dose, frequency and duration of each medication use will be collected. All data will be analysed in the same manner as described above (Response over time).

Safety parameters

Incidence rate of each adverse event is recorded and calculated. All data will be analysed in the same manner as described above (Response over time).

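### Section 10.2 assigns the Response over time methods, including a linear mixed model, to adverse event incidence and medication type, which they do not fit

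*Protocol*

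**What the plan says.** Section 10.2 sets out its methods under Response over time. Between arms it repeats the week 8 approach of section 10.1: Student t if normal, otherwise Mann-Whitney. Against baseline it uses paired t, Kruskal-Wallis or Mann-Whitney. It then adds a model: "Differences between treatments before and after supplement intake will also be analysed by linear mixed models for repeated measures". The model's time factor is 0, 4, 8, 12 and 60 weeks, subject is the random effect, and BMI, age, sex and medication use are to be taken into account.

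The later subsections point back to this block. Under Medication use: "Type, Dose, frequency and duration of each medication use will be collected", with all of it analysed in that way. Under Safety parameters: "Incidence rate of each adverse event is recorded and calculated", again with all data analysed in that way.

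For remission and response the wording is looser: "we will determine whether subjects have reached clinical remission and/or showed a clinical response over time". The data named for the within-subject tests that follow are the sum P-SCCAI score.

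Section 10 names no test for binary, count or nominal data. It says only that categorical data are presented as counts and percentages. It also fixes the threshold: "The threshold for significance will be set at $p<0.05$, with a FDR correction for 16S rRNA gene sequence data". Section 8.1.2 collects safety at weeks 0, 4 and 8, and medication at 0, 4, 8, 12 and 60. It reads a medication downgrade as improvement and an upgrade as worsening.

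**The concern.** The protocol does not leave the method open here. It prescribes one, and the prescription was written for a numeric score. Adverse event incidence is yes/no or count data, and medication type is a set of unordered labels. Followed literally, the text asks for the mean or rank of a label, for safety at visits where it is not recorded, and for a medication model adjusted for medication. Any p-value below 0.05 would be declared significant, because the only correction named is for sequencing data. Safety and medication statements could therefore rest on a model whose standard errors are wrong for the data.

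**Working it through.** **Inputs.** Arm sizes come from section 4.4: 11 per group before drop-out and 15 per arm enrolled, in four arms. The 11 reproduces by the normal approximation: n = 2(1.960 + 1.282)² × 0.5² / 0.7² = 2 × 10.51 × 0.25 / 0.49 = 10.7, rounded up to 11. The protocol gives no figure for the analyses discussed here and no event rates, so all rates below are assumptions.

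**Step 1. Does the cross-reference fit the data?**

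| Item | Response over time block | Adverse events | Medication |
|---|---|---|---|
| Scale | numeric score | yes/no or count | type unordered; dose, frequency and duration numeric |
| Time points | 0, 4, 8, 12, 60 | 0, 4, 8 | 0, 4, 8, 12, 60 |
| Covariates | include medication use | usable | outcome is also a covariate |

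The time points fail for safety. The scale and the covariate fail for medication type.

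**Step 2. Between-arm t and rank tests on yes/no data.** For a common event rate p, the type I error is the sum over all (a, b) of Bin(a; n, p) × Bin(b; n, p) for outcomes with p-value below 0.05. The maximum over p is:

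| n per arm | Student t | Mann-Whitney | Fisher |
|---|---|---|---|
| 11 | 5.3% | 5.3% | 1.7% |
| 15 | 5.5% | 4.3% | 1.8% |
| 30 | 5.5% | 5.5% | 2.7% |

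At a 5% event rate with 15 per arm, t and Mann-Whitney both give 0.5%. In simulated paired yes/no data with 15 or 30 subjects, paired t gave 2.5% to 4.8%. Mann-Whitney misapplied to correlated pairs gave about 1% to 1.6%, a loss of power. None of these tests shows material inflation.

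**Step 3. Linear mixed model on yes/no data.** A random-intercept model has one total variance for all weeks. Yes/no data have variance p(1 − p), which changes with the week's rate. For an arm contrast at one week, let R be that week's p(1 − p) divided by its mean over all weeks. The true type I error is then about 2 × [1 − Φ(1.96/√R)].

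Worked case, rates 0%, 20%, 40% at weeks 0, 4, 8: the variances are 0, 0.16 and 0.24, with mean 0.1333. R = 0.24/0.1333 = 1.80, 1.96/√1.80 = 1.461, and the type I error is about 14.4%.

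The same formula at week 8, beside simulations with no treatment effect (8,000 runs each, four arms):

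| Assumed rates by week | R | Formula | Simulated, 11 / 15 per arm |
|---|---|---|---|
| Safety 3, 5, 5% | 1.148 | 6.7% | 6.8% / 6.5% |
| Safety 5, 30, 30% | 1.348 | 9.1% | 10.0% / 7.8% |
| Safety 0, 20, 40% | 1.800 | 14.4% | 13.2% / 12.1% |
| Remission 0, 30, 40, 40, 40% | 1.290 | 8.4% | 7.4% / 9.8% |
| Remission 0, 5, 40, 20, 20% | 1.975 | 16.3% | 13.2% / 14.9% |

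A further simulation with rates that differ between weeks gave 15% to 19%. Treatment-by-time change contrasts stayed at 3.0% to 4.7%, and the overall arm-by-time test at 3.8% to 6.7%. The inflation thus belongs to single-week arm contrasts at weeks with above-average variance. At weeks with below-average variance the same mechanism makes the test too strict.

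**Step 4. Is the pattern of rates plausible?** For clinical response a zero at week 0 is built in, because response is a fall from baseline. For remission it nearly is, since entry requires a score of 3 to 5 and remission is 2 or below. This matters only if the yes/no status is put into the model. The later rates are assumed.

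**The case against.** The strongest counter-case is that the harm is small and partly imagined, and much of it stands.

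- A reader might infer that the t and rank tests create false significance. Step 2 does not support this. With few events they are conservative. The plan's own normality check would in any case reject a t-test: a 4/15 yes/no sample gives a Shapiro-Wilk p of about 0.00001, which leads to Mann-Whitney.
- A reader might point to 0/15 against 4/15 events, where Student t gives p = 0.032, Mann-Whitney 0.038 and Fisher 0.10. That gap mostly reflects Fisher's conservatism. Boschloo's exact test gives about 0.043, next to Mann-Whitney. The comparison is not evidence of a false positive.
- A reader might infer that yes/no remission and response are assigned to the same tests. The text names the sum P-SCCAI score as the data, so this is an ambiguity. A missing binary test could also be left to a statistical analysis plan that is not at hand.
- Dose, frequency and duration are numeric, so the scale objection does not reach them. The upgrade/downgrade reading in section 8.1.2 is ordered, and rank tests can handle it.
- These are secondary outcomes, and categorical data are already to be shown as counts and percentages.

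What the counter-case does not remove is the written instruction. All safety data and all medication data are sent to a block that includes a linear mixed model with the wrong visits and a circular covariate.

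**Conclusion.** The point holds for adverse event incidence and medication type. The cross-reference prescribes methods that do not suit unordered or yes/no data, a time factor with two visits at which safety is not collected, and a medication model adjusted for medication use. Those three mismatches follow from the text alone and need no assumption.

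The numerical harm is confined to single-week arm contrasts from the linear mixed model: roughly 6.5% to 19% type I error at a nominal 5%. In the simulated safety scenarios it was 6.5% to 13.2%. These figures depend on assumed event rates, on a single residual variance, and on yes/no coding at each visit. Where rates are low and steady the excess is slight. The between-arm t and rank tests are not at fault. For remission and response the text needs clarifying and is not plainly wrong. The primary analysis is unaffected. The text should be corrected, but the issue does not threaten the trial's main conclusion.

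**What to change.** In section 10.2:

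- **Safety parameters.** Delete the cross-reference. Report, by arm and at weeks 0, 4 and 8, the number and percentage of participants with each adverse event, with exact intervals for the risk difference and no mixed model.
- **Medication use.** Delete the cross-reference for type. Tabulate type by arm. Analyse change as upgrade, no change or downgrade, as section 8.1.2 already defines it, with an ordinal or exact test and without medication use as a covariate.
- **Response over time.** State that the listed tests and the linear mixed model apply to the P-SCCAI score. If yes/no remission and response are compared between arms, use a risk difference with exact interval or a logistic mixed model. If a test is wanted, an unconditional exact test such as Boschloo's avoids Fisher's conservatism.

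The change affects analysis text only, not conduct, visits or sample size. It costs slightly more analysis work, and with 11 to 15 per arm the exact intervals will be wide. A logistic mixed model may not be estimable if events are few, so the risk difference should be the default.

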10.3 Other study parameters

Habitual food intake

Data from FFQ will be analysed in the same manner as described above (Response over time). Also, it will be used for Pearson r correlation coefficient calculation, or a Spearman rank when not normally distributed, with other parameters.

Participants demographics and characteristics

Data will be analysed in the same manner as described above (Response over time).

Correlational analysis will be used to explore possible associations between symptoms and baseline characteristics.

10.4 Interim analysis (if applicable)

Not applicable.

11. ETHICAL CONSIDERATIONS

11.1 Regulation statement

This study will be conducted according to the principles of the Declaration of Helsinki (64th WMA Assembly, October 2013), and in accordance with the Medical Research Involving Human Subjects Act (WMO 1998), and other guidelines, regulations and acts.

11.2 Recruitment and consent

There are more than 1200 IBD patients in the patients base of Ziekenhuis Gelderse Vallei (ZGV). With around half UC patients have mild activity, this guarantees that enough potential patients will be reached out. Previous surveys performed in ZGV on dietary beliefs and behaviors showed that around 60% of IBD patients believe that diet could make a difference on the disease course. This increases the chance to involve enough patients who actually support the dietary strategy.

Recruitment will be done by the investigators. During the outpatient clinic visit, the UC patients of ZGV will be informed by nurses about this study. For questions, potential subjects can contact the investigators through e-mail or phone for further explanation of study procedures. Only when the patients agree to participate the study, their contact information will be shared with investigators, who will send the invitation for information meeting. Interested subjects will be invited for (digital) information events, where additional information will be given, and subjects have the chance to ask questions. After the information event, subjects have two weeks to decide whether they are interested in participating or not. If they wish to enter the study, they are asked to sign the informed consent form at home, and then send it to the researcher. The participants will be notified in the consent form to give permission to share the information of unexpected new findings regarding the (future) health of them with their General Practitioner (GP). The subject will receive a copy of the signed informed consent directly after signing. After this, subjects will receive the fecal material collection kit and information to provide the first fecal sample for pre-screening. Then within one week, subjects will receive packages with corresponding products and instructions.

Data will be stored at secured hard drives of Wageningen University, and will be locked with a password. Only members of the research team will have access to these data and only after they sign a confidentiality agreement. Paper data such as informed consent will be stored in a cabinet with a lock. Subjects will be given a study code, and only members of the research team will have access to the files decrypting the study code.

11.3 Objection by minors or incapacitated subjects (if applicable)

Not applicable.

11.4 Benefits and risks assessment, group relatedness

There is negligible risk for the participants. Dietary prebiotics has been proved to help with remission in UC patients. Participants may potentially benefit from the dietary intervention with improved disease activity.

Intervention products

The prebiotics used in this study has been *in vitro* tested to be effective in boosting butyrate production in healthy individuals and it also showed the same ability in mild UC patients *in vitro* beforehand. Maltodextrin and corn starch as a placebo has been widely used in many clinical trials, no adverse effects has been reported.

Time investment research participants

Research participants will invest approximately 9 hours during the trial. A schematic overview of the time investments is listed in **Table 2**.

Table 2: Overview of time investment of the research subjects

Items	Time (minutes)	Number	Time in total
Information meeting	60	1	60
Taking supplement	2	105	210
Long questionnaire	45	1	45
Short questionnaires	3-5	40	160
Stool collection	15	5	75
Total investment			550 min ≈ 9 hours

11.5 Compensation for injury

The sponsor/investigator has a liability insurance which is in accordance with article 7 of the WMO. The sponsor (also) has an insurance which is in accordance with the legal requirements in the Netherlands (Article 7 WMO). This insurance provides cover for damage to research subjects through injury or death caused by the study. The insurance applies to the damage that becomes apparent during the study or within 4 years after the end of the study.

11.6 Incentives

Based on burden calculations, after completion of the full study, each participant will receive a financial compensation of €105,-. Participants not selected for the study after the screening will receive €17. Research participants are free to withdraw from further participation for any reason and at any time during the trial and will receive a proportional repayment for the effort they made. However, if a participant needs to withdraw because of adverse events, or because of medical advice, he or she would receive the full financial compensation.

12. ADMINISTRATIVE ASPECTS, MONITORING AND PUBLICATION

12.1 Handling and storage of data and documents

Before the start of the study, subjects will be assigned to a study code that will not change during the study. This number is linked with the name, address, date of birth, and telephone number of the subject in a password-protected file that is stored separately from the study data. Only members of the research team involved in the study logistics (e.g. collecting samples) can access this file. For all other purposes, the study code will be used for subject identification. The informed consent will be stored separately from all other information. All researchers have signed a confidential statement. The handling of personal data will be done according to the General Data Protection Regulation (GDPR), which is enforced on the 25th of May 2018. According to standard data management procedures, all research data are stored for a period of 10 years after collection.

Thereafter, data and documents will be deleted and destroyed (e.g. by a shredder).

Biological samples will be stored for a maximum of 10 years after study end, defined as the last data collection point, and then disposed of according to biomedical waste procedures. In case we want to use the collected material for additional research, which includes research in relation to the health of the patients or other research activities that are not covered by this study, we will provide our plans to the medical ethics committee Oost Nederland for evaluation.

12.2 Monitoring and Quality Assurance

Not applicable.

12.3 Amendments

Amendments are changes made to the research after a favourable opinion by the accredited METC has been given. Non-substantial changes (such as typing errors, administrative changes like changes in names, telephone numbers and other contact details of involved persons mentioned in the submitted study documentation) will not be notified to the reviewing METC and the competent authority, but will be recorded and filed by the sponsor.

Substantial amendments will be notified to the METC that gave a favourable opinion. The documentation that will be included in the submission should cover the following information:

- Covering letter, including the reasons for the amendment in one or two sentences, a brief description of the changes that are included in the amendment and the name of the documents that are modified;
- An extract of the modified documents, where applicable, showing both the previous and new wording, where applicable;
- The new version of the modified documents, where applicable, identified with updated number of version and date.

